14.2.9 Total Days in the Hospital and Time to Hospital Discharge

Total days in the hospital will be based on data collected on the ‘Hospitalization’ eCRF page.

Total days in the hospital are defined as the sum, for all hospitalization events, of the time from first dose to the date of hospital discharge, in days:

- Total days in the hospital (days) =
 First hospitalization: *Date of hospital discharge – Day 1 + 1*
 +
 Subsequent hospitalization: *Date of discharge – date of admission + 1*

In other words, in case of hospital admission prior to and discharge after first dose, date of first dose will be used in place of date of hospital admission for calculation of total days in the hospital. In case of multiple hospitalizations, the total number of days of each event will be added up.

The following information will be presented:

- Number and percentage of participants with more than one hospital admission (only non-consecutive hospitalization will be included in the count)
- Number and percentage of participants in the following discharge categories: death in hospital, discontinuation in hospital, discharged from hospital.
- Summary statistics of duration of hospital stay.

In addition, time to hospital discharge will be based on data collected on the ‘Hospitalization’ eCRF page from Day 1 through Day 28.

The time to hospital discharge, defined as the time from first dose (Day 1) to the date of first hospitalization discharge, in days:

- Time to hospital discharge (days) = (Date of first hospitalization discharge – Date of first dose)

The rules for the different types of censoring/event below will be followed:

| # | Description | Date of Event or Censoring | Outcome |
|---|-------------|----------------------------|---------|
|---|-------------|----------------------------|---------|

| | | | |
|---|---|--|----------|
| 1 | Death from Day 1 up to D60/Study completion | D28 | Censored |
| 2 | Failure at any point and time during the study from D1 up to D28, defined as: * ICU admission leading to treatment discontinuation * use of mechanical ventilation * relapse | D28 | Censored |
| 3 | Hospital discharge before Day 28 | Date of hospital discharge | Event |
| 4 | No hospital discharge before Day 28/discontinuation without death or failure | Earliest between D28 and date of discontinuation | Censored |

Analyses will be performed as specified in Section 14.2.3.

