To assess the length of hospital stay with M5049 compared to placebo.	
 • Total days in the hospital from Day 1 through Day 60. • Time to hospital discharge from Day 1 through Day 28.
To evaluate modulation of biomarkers of COVID-19 inflammation with M5049 compared to placebo.	Inflammatory biomarkers (CRP, d-dimer, and ferritin) during study period (Day 1 through Day 28).
To evaluate modulation of select biomarkers with M5049 compared to placebo.	Biomarkers (IL-6, TNF α , IL-8) during study period (Day 1 through Day 28).
To evaluate occurrence of relapse with M5049 compared to placebo.	Occurrence of relapse in participants during the study period (if first discharged within the 60-day study period). Relapse refers to worsening oxygenation, with either a positive result of any respiratory pathogenic nucleic acid test, or worsening lesions on chest imaging with re-hospitalization.
To assess occurrence of re-hospitalizations due to COVID-19 disease complications.	Occurrence of re-hospitalization in participants during the study period (if first discharged within the 28-day study period) due to COVID-19 disease complications (Day 5 through Day 60).

OBJECTIVES	ENDPOINTS (OUTCOME MEASURES)
evaluate WBC as markers for disease severity.	

AESI = adverse event of special interest; COVID-19 = coronavirus disease 2019; CRP = C-reactive protein; C_{through} = predose observed concentration; ECG = electrocardiogram; ECMO = extracorporeal membrane oxygenation; ICU = intensive care unit; IFN = interferon; CCI [REDACTED]; PK = pharmacokinetic; CCI [REDACTED]; RRT = rapid response team; SAE = serious adverse event; SARS-CoV = severe acute respiratory syndrome coronavirus; SpO₂ = peripheral capillary oxygen saturation; TEAE = treatment-emergent adverse event; WBC = white blood cell.

4 Study Design

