10.4.3.9 Analysis of Total Days in the Hospital and Time to Hospital Discharge

The total number of days in the hospital from Day 1 through Day 60 will be described together with 95% CI by treatment group.

In addition, time to hospital discharge will be analyzed. The time to hospital discharge is defined as the time from first dose (Day 1) through Day 28 to hospital discharge. For participants who die and those considered as failure (that includes use of mechanical ventilation, ICU admission leading to treatment discontinuation, and relapse), the time to hospital discharge will be censored at Day 28. For participants completing the study without being discharged or failure, the time to hospital discharge will be censored at Day 28. Participants withdrawn before the End of Study Visit without hospital discharge or failure will be censored at the last date of available clinical status assessment.

[figure not shown]
Cumulative distribution function for time to hospital discharge will be estimated via the Kaplan-Meier (product-limit estimates) method by treatment group and presented together with associated statistics (median time to hospital discharge, hospital discharge rates at Day 7, Day 14, and Day 28) including the corresponding two-sided 95% CI.

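### SAP 14.2.9 gives no rule for death in total days in hospital, so deaths either count as completed stays or drop out, and the arm with more early deaths can show the lower mean stay

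*SAP*

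**What the plan says.** Protocol 3.2 sets a comparative objective: "To assess the length of hospital stay with M5049 compared to placebo". It has two endpoints, total days in hospital through Day 60 and time to hospital discharge through Day 28. For the first, Protocol 10.4.3.9 says: "The total number of days in the hospital from Day 1 through Day 60 will be described together with 95% CI by treatment group". It does not say what happens when a participant dies.

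SAP 14.2.9 has total days "defined as the sum, for all hospitalization events, of the time from first dose to the date of hospital discharge". The first stay is computed as "Date of hospital discharge – Day 1 + 1", and later stays are added from admission to discharge. It then tabulates three discharge categories, "death in hospital, discontinuation in hospital, discharged from hospital", and gives summary statistics of duration. Deaths are not excluded, given a value or treated as a competing event.

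For time to discharge, the same section does have a death rule. The row "Death from Day 1 up to D60/Study completion" is censored at D28, so a participant who dies is carried as not discharged.

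SAP 9.8 imputes a hospital discharge date only when the day is missing (to the last day of the month) and otherwise leaves it alone. It does not mention death there, although its rule for ICU discharge times does use the time of death as a limit.

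**The concern.** The formula needs a discharge date, and a participant who dies in hospital may or may not have one recorded. If the date of death is entered as the end of the stay, which the discharge categories make plausible, a death on Day 5 contributes 5 days and looks better than a recovery with discharge on Day 12. If no date is entered, the death drops out and the arms are compared among survivors only. Either way, death does not count against an arm under an objective that compares length of stay with placebo.

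This is out of step with the rest of the SAP. Death is carried to Day 28 as not recovered (14.1.1), not improved (14.2.3) and not discharged (14.2.9). It makes the participant a non-responder (14.2.1), is scored 8 on the clinical status scale at later timepoints (14.2.2), and is an event for ICU admission and ventilation (14.2.5 to 14.2.7). Total days in ICU (14.2.8) shares the gap.

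In-hospital withdrawal raises the same difficulty: it is a discharge category, it can cut the total short, and no rule says how the unobserved days are counted.

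**Working it through.** The documents give no expected stay, mortality rate or target difference for this endpoint, so there is no stated figure to reproduce. The check is what the formula does to the arm means.

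**Inputs.** From Protocol 4.1: 150 participants, 1:1:1, hence n = 50 per arm. Assumed, because the documents do not give them: survivor stay L (the same in both arms), number of deaths d, and day of death t.

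**Formulas.**
- Stay ends at death: arm mean = (d × t + (n − d) × L) / n. The difference between arms A and P is (dA − dP)/n × (t − L). Its sign depends only on whether deaths fall before or after the usual survivor stay ends.
- Deaths drop out: arm mean = L in both arms, difference 0.
- Days alive and out of hospital through Day 60, death = 0: arm mean = (n − d) × (60 − L) / n.

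**Illustration: L = 12, t = 5, 2 versus 7 deaths.**
- Stay ends at death: (48 × 12 + 2 × 5)/50 = 11.72 versus (43 × 12 + 7 × 5)/50 = 11.02. The arm with five more deaths looks 0.70 day better.
- Deaths drop out: 576/48 = 12 versus 516/43 = 12. No difference.
- Days alive and out of hospital: 48 × 48/50 = 46.08 versus 43 × 48/50 = 41.28. The same arm is 4.80 days worse.
- Medians: total days 12 in both arms, days alive and out of hospital 48 in both. Neither moves, because most participants share one value.

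**Range: 8 versus 2 deaths, arm with 8 minus arm with 2, in days.**

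| Survivor stay | Mean total days, deaths on Day 3 | Day 7 | Day 14 | Day 25 | Days alive and out of hospital (any death day) |
|---|---|---|---|---|---|
| 10 | −0.84 | −0.36 | +0.48 | +1.80 | −6.00 |
| 16 | −1.56 | −1.08 | −0.24 | +1.08 | −5.28 |

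For example, (8 − 2)/50 × (7 − 10) = −0.36, and for the last column −(8 − 2)/50 × (60 − 10) = −6.00. With 5 versus 2 deaths every entry is halved.

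**When survivor stays vary.** Stays were simulated as log-normal with median 10 and log-scale SD 0.6 (assumed), with 8 versus 2 deaths and 4,000 repetitions. The average differences in total days, with stays ending at death, were:

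| Day of death | Mean | Median | Share of simulated trials where the mean favours the arm with more deaths |
|---|---|---|---|
| 4 | −0.99 | −1.02 | 75% |
| 7 | −0.65 | −1.00 | 67% |
| 20 | +0.94 | +1.27 | 25% |

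Scoring each death as 60 hospital days instead gave about +5.7 in the mean and +1.2 to +1.3 in the median, against the arm with more deaths at every death day. So the median is not immune. It stays put when deaths are few and stays are tightly grouped, and shifted by about a day with this larger imbalance and spread.

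**The case against.** The strongest reply is that little hangs on this figure. Protocol 10.4.3.9 asks for a description by arm, SAP 14.2.9 specifies no between-arm estimate for total days, and SAP 9 says that there is no hypothesis testing. Deaths in hospital are tabulated beside the duration summary, and mortality through Day 60 is reported by arm (14.2.4). The endpoint under this objective that gets a log-rank test and hazard ratios, time to discharge, does handle death. The in-hospital versus discharged split in 14.2.2 counts death as not discharged at visits to Day 60, provided that each level has at least 6 participants. A plain bed-day count is also a legitimate measure of health-care burden, which the Protocol's rationale mentions. All of this stands and limits the severity.

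It does not remove the point. Time to discharge uses the first discharge and stops at Day 28, and the in-hospital split is a snapshot at each visit. Total days is the only length-of-stay measure that covers readmissions and Days 29 to 60. A separate mortality table does not correct the direction of a mean printed elsewhere.

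Three stronger readings are tempting. A reader might infer that the SAP ends a stay at death. It does not say so; that is an inference from the discharge categories, and SAP 9.8 leaves room for a missing date. A reader might infer that excess deaths always shorten the mean and median stay. The range above shows that late deaths lengthen both, and in the illustration the median does not move. A reader might infer that the length-of-stay objective cannot be assessed at all. Time to discharge contradicts that.

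**Conclusion.** The point holds as a gap in the death rule. Under either reading of the SAP 14.2.9 formula, death is not counted as unfavourable, and under one of them the arm with more early deaths can show a lower mean stay. The misdirection is 0.7 day in the illustration and up to about 1.6 days in the range examined, where a death-inclusive summary would put the same arm 4.8 to 6.0 days worse.

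These sizes rest on assumed death counts, death days and survivor stays; the documents supply only the 50 per arm. The direction depends on deaths preceding the usual survivor stay, which the documents neither predict nor exclude. The importance is modest, because the endpoint is secondary and descriptive in an exploratory trial. It is still worth correcting before unblinding, since a death rule chosen afterwards would be open to the charge of being driven by the data.

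**What to change.** In SAP 14.2.9:

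1. Add days alive and out of hospital through Day 60, with 0 for anyone who dies by Day 60, as the summary used to compare arms on length of stay. Report the mean and median by arm, and the mean difference of each dose versus placebo with a 95% CI. The mean has to be shown because the median alone would show no difference in the illustration.
2. State how participants who withdraw while in hospital are counted. One option is to treat the days after withdrawal as missing, with a sensitivity analysis that counts them as hospital days.
3. Keep raw total days in hospital as the protocol's descriptive line with its 95% CI, shown by discharge category (death, discontinuation, discharged), and say what date ends the stay of a participant who dies.

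Adding the composite beside the bed-day count leaves the protocol's endpoint in place. The cost is SAP wording and one derived variable from the Hospitalization and Death eCRF pages, both already in use. The small downside is that the composite is no longer a plain bed-day count, which is why the raw figure stays. Total days in ICU (14.2.8) would benefit from a matching statement on death.

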14.2.10 Inflammatory Biomarkers

Inflammatory biomarker analysis will be based on data collected on the ‘Inflammatory biomarkers’ eCRF page and will be performed based on the PDAS.

The following inflammatory biomarkers will be collected for this study and analyzed by a local laboratory as per the schedule of events reported in the protocol:

- C-Reactive Protein, D-dimer, Ferritin

The following summaries will be provided by treatment group and total based on the PDAS for each inflammatory biomarker:

- Observed, change and percent change from baseline by analysis visit;
- Box and whisker plots over time for observed, change and percent change from baseline by treatment group;
- Spaghetti plots of change and percent change from baseline by treatment group

CCI

CCI

CCI

CCI

CCI

CCI

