Routine hematology, chemistry	X	←---Once daily during hospitalization (incl. predose on Day 1). If discharged, then at study visits (e.g., Days 3, 5, 7, 10, 14, 21, 28) if participant returns to study site-----→													WBC with differential: numbers and percentage, Hgb, HCT, platelets; electrolytes, BUN, Cr, eGFR, albumin, glucose, TP, ALT, AST, CK (unless participant is discharged). See Appendix 4 . Labs obtained within 24 hours of Day 1 can be used for Day 1 assessments. Record results daily from the participant's chart (unless participant is discharged). Evaluations to be performed by local laboratory.
Inflammatory biomarkers tested in COVID-19 (CRP, d-dimer, and ferritin)	X	X		X		X	X	X	X		X			X	Record any available results (and time sample collected) from the participant's chart on days indicated (unless participant is discharged). Part A and Part B: Evaluations to be performed by local laboratory.

Assessments and Procedures	SCR	Intervention Period (Days)							Continued Surveillance		Safety Follow-up			Relapse Admission ^a	Notes
									HD/ET	EoT					
	(up to 48 hours before Day 1)														HD assessments should occur if participant discharged after Day 3 and before Day 14. ET (early termination of treatment) Visit should occur within + 24 hours of treatment discontinuation.
Study Day		1	2	3	5	7	10		14	21	28	44	60	5 to 60	
Visit Window			± 6 h		± 12 h		± 24 h			+ 2 days		± 5 days	± 7 days	± 6 h	
Predose PK		X		X		X									PK blood collection must be done within 60 minutes prior to dose administration. Identify and record the time of the closest meal consumed prior to the study intervention administration, i.e., when the last meal was finished before the study intervention administration (unless participant is discharged). PK evaluations to be performed by central laboratory.

Assessments and Procedures	SCR	Intervention Period (Days)							Continued Surveillance		Safety Follow-up			Relapse Admission ^a	Notes
		1	2	3	5	7	10	HD/ET	EoT	21	28	44	60		
	(up to 48 hours before Day 1)														HD assessments should occur if participant discharged after Day 3 and before Day 14. ET (early termination of treatment) Visit should occur within + 24 hours of treatment discontinuation.
Study Day		1	2	3	5	7	10		14	21	28	44	60	5 to 60	
Visit Window			± 6 h	± 12 h	± 24 h					+ 2 days	± 5 days	± 7 days	± 6 h		

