4.4 Early Hospital Discharge Assessments

A participant who is discharged from the hospital after Day 3 and before Day 14 should have the same assessments as ET of study treatments as per the schedule of assessments (Section 1.2), but continue study treatment as an outpatient until Day 14.

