4.7 Surveillance, Safety and End of Study Visits

Since important secondary endpoints are evaluated at Day 28, surveillance assessments occur between Day 14 and Day 28, which may be distinguished from continued safety follow-up to Day 60. If a participant is discharged and not seen at the study site (as may be the requirement of the state and/or local hospital/clinic), every effort should be made to collect what information is available over the phone or through a telemedicine contact after hospital discharge.

As the majority of study participants should be discharged by Day 28, assessments for visits at Day 44 and Day 60 (End of Study) are anticipated to be by telemedicine or phone contact.

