10.4.3.10 Analysis of Inflammatory Biomarkers

Absolute values, absolute changes, and percent changes from Baseline to each time point in inflammatory biomarkers will be summarized by treatment group.

Descriptive statistics will be displayed using Box and Whisker plots.

Spaghetti plots with percent change from Baseline as well as absolute change from Baseline will also be provided by treatment group.

10.4.3.12 Analysis of Occurrence of Relapse in Participants During the Study Period (if First Discharged Within the 60-day Study Period)

Count and percentage of participants with relapse (see Section 4.8 for definition) among participants discharged before Day 28 with 95% CI will be presented by treatment group.

10.4.3.13 Analysis of Occurrence of Re-hospitalization in Participants During the Study Period (if First Discharged Within the 60-day Study Period) Due to COVID-19 Disease Complications

Count and percentage of participants who are re-hospitalized before Day 28 with 95% CI will be presented by treatment group and whether or not due to COVID-19 disease complications.

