| To evaluate clinical deterioration with M5049 compared to placebo. | 
 • Time to ICU (Day 1 through Day 28). • Time to invasive mechanical ventilation (Day 1 through Day 28). • Time to noninvasive mechanical ventilation (Day 1 through Day 28). | 
 • 14.2.5 • 14.2.7 • 14.2.6 |
| To assess the length of stay in the ICU with M5049 compared to placebo. | Total days in ICU from Day 1 through Day 60. | 14.2.8 |
| To assess the length of hospital, stay with M5049 compared to placebo. | 
 • Total days in the hospital from Day 1 through Day 60. • Time to hospital discharge from Day 1 to Day 28 | 14.2.9 |
| To evaluate modulation of biomarkers of COVID-19 inflammation with M5049 compared to placebo. | Inflammatory biomarkers (CRP, d-dimer, and ferritin) during study period (Day 1 through Day 28). | 14.2.10 |
| To evaluate modulation of select biomarkers with M5049 compared to placebo. | Biomarkers (IL-6, TNF alpha, IL-8) during study period (Day 1 through Day 28). | 14.2.11 |
| To evaluate occurrence of relapse with M5049 compared to placebo. | Occurrence of relapse in participants during the study period (if first discharged within the 60-day study period). Relapse refers to worsening oxygenation, with either a positive result of any respiratory pathogenic nucleic acid test, or worsening lesions on chest imaging with re-hospitalization. | 14.2.12 |
| To assess occurrence of re-hospitalizations due to COVID-19 disease complications. | Occurrence of re-hospitalization in participants during the study period (if first discharged within the 60-day study period) due to COVID-19 disease complications (Day 5 through Day 60). | 14.2.13 |

AESI = adverse event of special interest; COVID-19 = coronavirus disease 2019; CRP = C-reactive protein; C_{trough} = predose observed concentration; ECG = electrocardiogram; ECMO = extracorporeal membrane oxygenation; IAP = Integrated Analysis Plan; ICU = intensive care unit; IFN = interferon; CCI [REDACTED]; PK = pharmacokinetic; CCI [REDACTED] RRT = rapid response team; SAE = serious adverse event; SARS-CoV = severe acute respiratory syndrome coronavirus; SpO₂ = peripheral capillary oxygen saturation; TEAE = treatment-emergent adverse event; CCI [REDACTED]

6 Overview of Planned Analyses

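### The CRP, D-dimer and ferritin objective is a comparison with placebo, but the visible analysis gives only by-arm summaries, with no dose-versus-placebo estimate or interval

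*SAP*

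**What the plan says.** The objective in SAP 5.2, repeated in protocol 1.1 and 3.2, is "To evaluate modulation of biomarkers of COVID-19 inflammation with M5049 compared to placebo". The endpoint is "Inflammatory biomarkers (CRP, d-dimer, and ferritin) during study period (Day 1 through Day 28".

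The protocol's analysis (10.4.3.10) reads "Absolute values, absolute changes, and percent changes from Baseline to each time point in inflammatory biomarkers will be summarized by treatment group", followed by box and spaghetti plots. SAP 14.2.10 uses the pharmacodynamic analysis set and has three matching bullets: "Observed, change and percent change from baseline by analysis visit", box plots over time, and spaghetti plots. Redacted blocks come directly after them.

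On data collection, the biomarker row of the Schedule of Assessments takes available results from the participant's "chart on days indicated (unless participant is discharged". The marked days after Screening are 1, 3, 7, 10, 14 and 28. The hospital-discharge/early-termination column is also marked, and protocol 4.4 says that a participant discharged after Day 3 and before Day 14 "should have the same assessments as ET of study treatments". SAP 9.8 uses data as observed, without imputation unless otherwise specified.

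**The concern.** An objective worded as a comparison with placebo needs an estimate of that comparison and a statement of its uncertainty. Three by-arm columns provide neither. If these markers fall in every arm as pneumonia resolves, which is likely but not stated in the documents, within-arm change mixes recovery common to all arms with any drug effect. Only the contrast with placebo separates the two.

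The contrast matters for reading this trial. Protocol 4.3 justifies the two doses partly by the chance of seeing a pharmacodynamic effect through suppression of inflammatory biomarkers. Without a prespecified contrast, a reader would subtract arm means informally, or a marker, visit and scale would be chosen after unblinding.

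The people contributing values also change over time. Protocol 4.7 plans its late visits on the basis that "As the majority of study participants should be discharged by Day 28". The later the visit, the more a by-arm summary describes those who have not yet gone home, and that subset can differ between arms if treatment affects discharge.

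**Working it through.** No sample size, effect size or SD is stated for these markers in the visible text, so there is no planned figure to reproduce. The check has four steps.

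**1. Objective against analysis.** The objective requires M5049 versus placebo. Protocol 10.4.3.10 and the visible part of SAP 14.2.10 contain no difference, ratio, confidence interval, model or baseline adjustment. SAP 9 sets a default that comparisons are each dose against placebo, with two-sided 95% intervals, but supplies no estimator for a skewed, repeatedly measured marker.

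**2. The same SAP elsewhere.**

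| SAP section | Dose-versus-placebo estimate with 95% CI |
|---|---|
| 14.1.1, 14.2.3, 14.2.5 to 14.2.7, time to discharge in 14.2.9 | Hazard ratio |
| 14.2.1 | Difference in proportions |
| 14.2.2 | Odds ratio |
| 14.2.4, 14.2.12, 14.2.13 | Difference in proportions, if more than 6 events |
| 14.2.8, total hospital days in 14.2.9 | None (by-arm summaries) |
| 14.2.10 | None visible |

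Most efficacy endpoints in this exploratory plan therefore get a contrast. The gap in 14.2.10 is not unique.

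**3. Who has a value at each visit.** Scheduled values stop at discharge. Discharge on Days 4 to 13 should also give one discharge sample. Under the SAP 9.9 windows it falls as follows:
- Days 4 to 6: Analysis Day 4 or 5, neither of which has a scheduled draw of these markers.
- Days 7 and 8: Analysis Day 7.
- Days 9 to 11: Analysis Day 10.
- Days 12 and 13: Analysis Day 14.

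Some discharged participants thus stay in the Day 7, 10 and 14 summaries, but each contributes one discharge value at most, and discharge from Day 14 onward has no such sample.

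If discharge is unrelated to the marker, this selection does no harm. If low values hasten discharge and the drug lowers values, the active-arm participants who remain are selected towards higher values and the contrast shrinks. The documents do not give the strength of that link. As an illustration only, a simulation used these assumptions, none from the documents:
- Mean decline in log CRP of 0.10 per day on placebo, and 0.03 or 0.06 per day steeper on M5049.
- Daily log-odds of discharge falling by 0, 0.5, 1 or 2 per unit of current log CRP.
- Runs with and without CRP-related deaths.
- No use of the discharge sample in the observed contrast.

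| Fall in discharge log-odds | Observed Day 14 contrast in log change, as share of true contrast |
|---|---|
| 0 | 99% to 100% |
| 0.5 | 95% to 97% |
| 1 | 87% to 91% |
| 2 | 79% to 83% |

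In one setting with the strongest link (steeper decline, no deaths), the true contrast was -0.78, the observed contrast -0.64, and a likelihood-type estimate assuming data missing at random -0.65. Because the discharge sample is left out, these figures do not describe the planned data. They show only that the effect can run from none to moderate, and that a model need not remove it.

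**4. Is a contrast feasible?** Protocol 4.1 plans 15 + 135 = 150 participants randomised 1:1:1, so 150 / 3 = 50 per arm. For an unadjusted difference between two arms, the 95% half-width is 1.96 × SD × √(2/n):
- n = 50: 1.96 × √(2/50) = 0.39 SD
- n = 25: 1.96 × √(2/25) = 0.55 SD
- n = 15: 1.96 × √(2/15) = 0.72 SD

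The values 25 and 15 are assumed numbers still sampled. The contrast is usable while most of an arm is sampled and becomes imprecise as numbers fall.

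**The case against.** The strongest reply is that the analysis may exist behind the redactions. Blocks are blacked out straight after the three bullets. MMRM is in the SAP abbreviation list with no visible use. Protocol numbering jumps from 10.4.3.10 to 10.4.3.12, so the lack of a redaction mark in 10.4.3.10 does not prove that its text is complete. This stands: a reader might infer that the placebo contrast is never estimated, but the documents support only that none is specified in the visible text. What favours a real gap is that the protocol text matches the three SAP bullets, and that neither SAP 7 nor the modification history mentions an added biomarker model.

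Second, the study is exploratory, SAP 9 already defaults to dose-versus-placebo comparisons, and total ICU and hospital days are descriptive too. That rules out any argument about error rates and lowers the priority. It does not supply an estimator for a stated objective.

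Third, SAP 9.1 already provides n, median, quartiles and range. A reader might infer that outliers in percent change make the output uninformative. With medians, quartiles, box plots and absolute change all planned, the documents do not support that.

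**Conclusion.** On the visible text, a secondary objective worded as a comparison with placebo has no specified comparison. That follows from the documents alone and needs no simulation. It is a mismatch between objective and analysis in an exploratory study, and the remedy is a cheap improvement.

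The selection argument is conditional. A reader might infer that the by-arm summaries will understate the drug effect. They could, if discharge depends on the marker, but the documents give no size, other selection mechanisms could act differently, and the discharge sample softens the problem. A reader might also infer that a repeated-measures model would cure any bias, or that most participants are still in hospital at Day 7. The first failed in the illustration above, and the documents do not state the second. Early visits are preferable because selection through discharge accumulates over time, not because any particular fraction is known to remain.

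**What to change.** If the redacted text after SAP 14.2.10 already specifies a between-arm analysis of CRP, D-dimer and ferritin, confirm that it does. Otherwise keep the summaries and plots and add one exploratory analysis per marker:

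- **Model:** the log-transformed value, by MMRM with log baseline, treatment, analysis visit, treatment-by-visit, corticosteroid stratum and country (the two factors kept in SAP 8.2). ANCOVA per visit is an acceptable simpler choice.
- **Data:** include discharge-visit samples under the SAP 9.9 windows, and say how those falling in Analysis Day 4 or 5 are used.
- **Report:** each dose versus placebo as a geometric mean ratio with two-sided 95% CI, with n per arm and visit beside it, emphasising Days 3 and 7.
- **Caveat:** state that later visits rest on few participants and on a missing-at-random assumption that may remove only part of any discharge-related bias.

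The cost is SAP wording and three exploratory models on data already collected. No visit, sample or participant is added.
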